PK	Pharmacokinetics
PPS	Per-Protocol Set
PR	Partial Response
Q2W, Q3W, Q4W	Respectively, every two, three, four weeks
RAP	Report and Analysis Process
RDI	Relative Dose Intensity
RECIST	Response Evaluation Criteria in Solid Tumors
RP2D	Recommended Phase two Dose
SAE	Serious Adverse Event
SAP	Statistical Analysis Plan
SOC	System Organ Class
TFL	Tables, Figures, Listings
TNBC	Triple Negative Breast Cancer
WHO	World Health Organization

1 Introduction

This Statistical Analysis Plan (SAP) provides detailed statistical methodology for the analysis of data from study CMCS110Z2102 that will be presented in the Clinical Study Report (CSR). The output shells (in-text and post-text) accompanying this document can be found in the Table Figure Listing (TFL) shells document. The specifications for derived variable and datasets can be found in the Programming Datasets Specifications (PDS) document.

All changes to the planned analysis described in this document required before or after database lock will be made through an amendment or addendum, respectively. Note that obvious corrections will be made at the time of analysis to address minor formatting or spelling mistakes present in the TFL shells document without the need to amend.

[figure not shown]
The SAP, TFL shells and PDS documents may also serve as a reference for the creation of any outputs required outside of the CSR, e.g., MTD/RP2D declaration, IB updates, abstracts, posters, presentations, manuscripts and management updates. Data used for these analyses will have a status aligned to the database lock guidance.

RAP documents, including SAP and TFL shells, were created based on final protocol version 05 released on 23 July, 2019.

1.1 Study design

This study is a phase Ib/II, multi-center, open-label study starting with a phase Ib dose escalation part followed by a phase II part. MCS110 and PDR001 will be administered i.v. every three weeks (Q3W) until the patient experiences unacceptable toxicity, progressive disease as per irRC and/or treatment is discontinued at the discretion of the investigator or the patient. Patients should not discontinue treatment based on progressive disease per RECIST v1.1. The study design is summarized in [Figure 1-1](#).

Figure 1-1 Study design

Phase Ib part

During the phase Ib part of the study, cohorts of patients will be treated with increasing doses of MCS110 and PDR001 every three weeks until a RP2D is determined for this treatment combination.

It is expected that an RP2D will be established before the MTD is reached. The RP2D for the combination will not exceed the RP2Ds for the single agent administration of MCS110 and PDR001. To assure that the combination RP2D does not exceed the MTD, combination MCS110 and PDR001 dose escalation will also be guided by an adaptive Bayesian logistic regression model (BLRM) following the escalation with overdose control (EWOC) principle. At least 15 patients are required during dose escalation to define the MTD; however, fewer than 15 patients may be treated if the RP2D is determined without reaching the MTD (for further details see [\[CMCS110Z2102-CSP-Section 6.2.3\]](#)).

Phase II part

Once the MTD and/or RP2D have been declared, additional patients will be enrolled in the Phase II part in order to assess the preliminary anti-tumor activity of MCS110 in combination with PDR001.

In the phase II part, patients will be assigned to different groups depending on the tumor type as shown in [Figure 1-1](#). Please refer to [\[CMCS110Z2102-CSP-Section 5.1\]](#) for further details.

All groups will enroll approximately 20 patients each. Enrollment to any of these groups may be stopped at fewer patients if achieving these enrollment targets is not logistically feasible. For groups 1 and 3, the sample size may be extended to approximately 40 patients, if at least 3 patients out of the first 20 treated in that group have an objective response (CR or PR) per RECIST v1.1 or irRC. Twenty patients will be enrolled into Group 2 at RP2D. Enrollment may be expanded up to approximately 40 patients if clinical benefit per RECIST v1.1 or irRC (CR, PR or SD > 4 months) is observed in at least 3 pts. In addition, an exploratory group of 20 patients at a lower dose (1 mg/kg MCS110 in combination with PDR001 300 mg) may be opened if the above mentioned gating criteria is met. Group 4 may similarly be expanded if at least 2 patients out of the first 20 treated in that group have an objective response. A Bayesian design will be used in order to estimate ORR within each expansion group. Details of the sample size calculations leading to the patient numbers are provided in [\[CMCS110Z2102-CSP-Section 10.8\]](#).

The primary CSR will be based on all patients' data from the phase Ib and phase II parts, up to the time when all patients have completed at least six cycles of treatment or discontinued treatment. Patients who are on study beyond cycle 6 may remain on treatment until they discontinue the study. Any additional data (after the data cut-off date for the primary CSR) will be further summarized in a final CSR at completion of the study, as defined in [\[CMCS110Z2102-CSP-Section 4.3\]](#).

[figure not shown]
1.2 Study objectives and endpoints

Objectives and related endpoints are described in [Table 1-1](#) below.

Table 1-1 Objectives and related endpoint

Objective	Endpoint	Analysis
Primary		
Phase Ib part:		
To characterize the safety and tolerability of MCS110 given in combination with PDR001 and to identify a recommended dose combination for Phase II.	Frequency, severity and seriousness of AEs, laboratory abnormalities and other safety parameters. Dose interruptions, reductions, and dose intensity.	Refer to Section 2.8
	Incidence rate of dose limiting toxicities (DLTs) during the first two cycles of study treatment.	Refer to Section 2.5.2.1
Phase II part:		
To estimate the anti-tumor activity of the combination of MCS110 with PDR001	-Overall response rate (ORR) per Response Evaluation Criteria in Solid Tumors (RECIST v1.1) (groups 1, 3 and 4). -Clinical benefit rate (CBR) per Response Evaluation Criteria in Solid Tumors (RECIST v1.1), which is defined as confirmed objective response or SD > 4 months. (Group 2)	Refer to Section 2.5.2.2
Secondary		
Phase Ib part:		
To estimate the preliminary anti-tumor activity of the combination of MCS110 with PDR001	ORR, progression free survival (PFS), clinical benefit rate (CBR), duration of response (DOR) and disease control rate (DCR) per RECIST v1.1 and per immune related Response Criteria (irRC)	Refer to Section 2.7
Phase II part:		
To further characterize the safety and tolerability of MCS110 given in combination with PDR001	Frequency, severity and seriousness of AEs, laboratory abnormalities and other safety parameters.	Refer to Section 2.8
Phase II part:		
To evaluate the preliminary anti-tumor activity of the combination of MCS110 with PDR001 by additional efficacy measures	ORR per irRC, PFS, DOR, DCR, CBR per RECIST v1.1 and per irRC (Group 1, 3 and 4) CBR per irRC, PFS, DOR, DCR, ORR per RECIST v1.1 and per irRC (Group 2)	Refer to Section 2.7
Phase Ib and Phase II parts:		
To characterize the pharmacokinetics of MCS110 and PDR001 in combination	Serum concentration of MCS110 and PDR001 and PK parameters	Refer to Section 2.9
To assess immunogenicity of MCS110 and PDR001	Presence and/or concentration of anti-PDR001 or anti-MCS110 antibodies	Refer to Section 2.9

Objective	Endpoint	Analysis
To describe survival with MCS110 and PDR001 in combination	Overall survival (OS)	Refer to Section 2.7

2 Statistical methods

2.1 Data analysis general information

The data will be analyzed by Novartis personnel and/or designated CRO(s) using SAS version 9.4, for Bayesian logistic regression model (BLRM) modeling, R version 3.0.2 and JAGS version 3.12 will be applied and for other bayesian analyses, R version 3.4.3 will be used. PK parameters will be calculated using non-compartmental methods available in Pharsight

Phoenix version 6.4 (or newer compatible version). Newer compatible version may be used for all programs. Any data analysis carried out independently by the investigator must be submitted to Novartis before publication or presentation.

It is planned that the data from participating centers in this protocol will be combined, so that an adequate number of patients will be available for analysis. The data will be summarized with respect to demographic and baseline characteristics, efficacy observations and measurements, safety observations and measurements, and all relevant PK and PD measurements using descriptive statistics (quantitative data) and contingency tables (qualitative data).

The study data will be analyzed and reported based on all patients' data of the Phase Ib and Phase II parts up to the time when all patients have potentially completed at least six cycles of treatment or discontinued the study. Phase Ib data and Phase II data will be reported separately. Any additional data for patients continuing to receive study treatment past the data cutoff date for the primary CSR, as allowed by the protocol, will be reported at completion of the study as defined in [\[CMCS110Z2102-CSP-Section 4.3\]](#).

The following rules will be followed for reporting results unless stated otherwise:

- Phase Ib dose escalation data: cohorts treated during the dose escalation with the same dose levels of MCS110 and PDR001 will be pooled into a single treatment group. All summaries, listings, figures and analyses will be performed by treatment group and “All Phase Ib Subjects”.
- Phase II data: All summaries, listings, figures for non-safety analysis will be reported by arm. Safety analysis of phase II will be reported by arm and “All Phase II Subjects” Column. The arms to which they were assigned at baseline based on disease types consist of the following:
 - Group 1: TNBC (naive to PD-1/PD-L1 directed therapy)
 - Group 2: Pancreatic cancer (naive to PD-1/PD-L1 directed therapy)
 - Group 3: Endometrial cancer (naive to PD-1/PD-L1 directed therapy)
 - Group 4: Melanoma (resistant to PD-1/PD-L1 directed therapy)

Categorical data will be presented as frequencies and percentages. For continuous data, mean, standard deviation, median, minimum, and maximum will be presented.

Screen failure patients are those who signed the informed consent, but never started the study treatment for any reason. For these patients, the eCRF data collected (see [\[CMCS110Z2102-CSP-Section 7.1.1.1\]](#)) will not be included in analyses, but will be reported in the CSR as separate listings.

2.1.1 General definitions

Study drug and Study treatment

Study drug refers to the individual compound i.e., MCS110, or PDR001. The study treatment is defined as MCS110 in combination with PDR001, or single agent MCS110 or PDR001 if one of the study drugs needs to be discontinued.

Date of first/last administration of study drug and study treatment

The date of first (last) administration of study drug is derived as the first (last) date when a non-zero dose of study drug was administered and recorded on the Dosage Administration Record (DAR) eCRF.

The date of first (last) administration of study treatment is derived as the first (last) date when a non-zero dose of any component of study treatment was administered and recorded on the Dosage Administration Record (DAR) eCRF. Dates of first/last administration of study treatment are defined as:

- Date of first administration of study treatment = min (first date of MCS110 administration, first date of PDR001 administration)
- Date of last administration of study treatment = max (last date of MCS110 administration, last date of PDR001 administration)

Study day

The study day for all assessments/events will be calculated using the start date of study treatment as reference. For assessments/events occurring on or after the start date of study treatment, study day will be calculated as:

Study day (days) = Event date – Start date of study treatment + 1

Therefore, the first day of study treatment is study day 1.

For all assessment/events occurring prior to the start of the study treatment, study day will be negative and will be calculated as:

Study day (days) = Event date – Start date of study treatment

Study day will be displayed in the data listings.

Baseline

Baseline is the last available and valid assessment performed or value measured within 21 days (28 days for baseline radiological evaluations) before the first administration of study treatment, unless otherwise stated under the related assessment section. Baseline can be the day before first treatment administration or the same day as first treatment administration if a pre-dose assessment/value is available (e.g., ECG, PK samples, [REDACTED]).

If time is recorded for the first treatment dose and for a specific assessment performed the day of first dose, this assessment will be considered as baseline only if it is actually performed before the first dose, as checked using both times.

If time is not recorded, a specific assessment performed the day of first dose administration will be considered as baseline if, according to protocol, it should be performed before the first dose.

[REDACTED]

Patients with no data on a particular parameter before the first treatment administration will have a missing baseline for this parameter.

For pregnancy test, baseline will be within 72 hours before first administration of study treatment.

Computation of baseline for ECG, [REDACTED] and other endpoints are described in each specific section.

On-treatment assessment/event

An on-treatment assessment/event is defined as any assessment/event obtained in the time interval from the start date of study treatment until the last date of study treatment (i.e., including combination partner) + 30 days inclusive.

Any assessments taken more than 30 days after the last dose of study treatment will not be included in the best overall response derivation. If any alternative cancer therapy is taken while on study any subsequent efficacy assessments would be excluded from all relevant efficacy summary.

2.2 Analysis sets/Withdrawal of ICF/Subgroups

2.2.1 Full Analysis Set

The full analysis set (FAS) comprises all patients who received at least one dose of MCS110 or PDR001. Patients will be analyzed according to the planned treatment combination. Unless otherwise specified, FAS is the default set used for all analyses.

2.2.2 Safety Set

The safety set (SS) includes all patients who have received at least one dose of MCS110 or PDR001. Patients will be classified according to treatment received, where treatment received is defined as:

1. The treatment assigned if it was received at least once, or
2. The first treatment received when starting therapy with study treatment if the assigned treatment was never received.

The safety set will be used for the safety summary of the study.

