6.2.3.2 Intra-Patient dose escalation

Intra-patient dose escalation is not permitted at any time within the first 6 months of treatment. After the 6 months of treatment is completed, individual patients may be considered for treatment at doses of MCS110 and PDR001 in combination higher than the doses to which they were initially assigned. Only one of the study drugs will be escalated at any one time. Study drugs will be escalated as detailed in [Section 6.2.2](#). In order for a patient to be treated at a higher treatment dose, he or she must have tolerated the lower dose of MCS110 and PDR001 combination for at least two cycles of therapy (e.g., he or she must not have experienced a toxicity of CTCAE Grade ≥ 2 at the lower dose pair for which relationship to study drug cannot be ruled out). Moreover, the new, higher dose pair with which the patient is to be treated must be a dose pair that has completed evaluation in a dose-escalation meeting and that has satisfied the EWOC criterion under the Bayesian model.

There is no limit to the number of times a patient may have his or her treatment dose increased. Any further increases after the initial intra-patient dose escalation are subject to the same rules as for the initial intra-patient escalation. Consultation with Novartis must occur prior to any

intra-patient dose escalation occurring. These changes must be recorded on the Dosage Administration Record CRF.

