2.4.1 Study treatment/compliance

Study treatment

MCS110 in combination with PDR001 (Q3W):

- Last date of *exposure* to study drug (MCS110) = last date of administration of MCS110 + 20 days
- Last date of *exposure* to study drug (PDR001) = last date of administration of PDR001 + 20 days
- Last date of *exposure* to study treatment (MCS110 + PDR001) = max (last date of MCS110 administration, last date of PDR001 administration) + 20 days = Date of last administration of study treatment + 20 days

Planned treatment: Planned treatment is the treatment to which a patient is assigned during enrollment.

Received treatment: Please refer to [Section 2.2.2](#).

Planned dose: Planned dose is the dose level(s) of study drug(s) corresponding to the planned treatment.

Prescribed dose: Prescribed dose is the dose level(s) of study drug(s) prescribed by doctor before study treatment is administered at beginning of each cycle.

Dose administered (mg/kg) for MCS110 = Dose prescribed (mg/kg) * Total volume administered (mL)/Total volume planned to be administered (mL);

Dose administered (mg) for PDR001 = Dose prescribed (mg) * Total volume administered (mL)/Total volume planned to be administered (mL);

Definitions of duration of exposure, cumulative dose, actual dose intensity (DI), planned dose intensity (PDI), relative dose intensity (RDI), as well as intermediate calculations, are as follows:

- **Duration of exposure (days) to study drug:** last date of *exposure* to study drug – first date of study drug + 1 (periods of interruption are not excluded);

- **Duration of exposure (days) to study treatment:** last date of *exposure* to study treatment – first date of study treatment + 1 (periods of interruption are not excluded);
- **Duration of exposure (weeks)** = Duration of exposure (days)/7;
- **Cumulative dose:** sum of all dose administered (mg/kg) to a patient for MCS110; sum of all dose administered (mg) to a patients for PDR001;
- **Cumulative planned dose:** sum of all planned dose (mg/kg) of MCS110 that were intended to have been taken during the treatment period by a patient; sum of all planned dose (mg) of PDR001 that were intended to have been taken during the treatment period by a patient;

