- **Number of doses scheduled per protocol :** number of doses given to a patient if each actual cycle length is exactly 21 days and study treatment is given on day 1 of each cycle, which is calculated as: [Duration of exposure to study drug (days)/ 21 (days)] + 1*I{ Duration of exposure to study drug (days) mod 21 (days) ≠ 0}. [x] is the largest integer less than or equal to x. $b = \text{mod}(a, m)$ returns the remainder after division of a by m , where a is the dividend and m is the divisor. I{·} is a indicator function. This will be calculated for MCS110 and PDR001 separately and used for calculation of dose intensity below.
- **DI:**
 - For MCS110 (mg/kg/3wks): cumulative dose (mg/kg)/ number of doses scheduled per protocol during treatment period;
 - For PDR001 (mg/3wks): cumulative dose (mg)/ number of doses scheduled per protocol during treatment period;
- **PDI:**
 - For MCS110 (mg/kg/3wks): cumulative planned dose (mg/kg)/ number of doses scheduled per protocol during treatment period (i.e., this is equivalent to planned dose level);
 - For PDR001 (mg/3wks): planned cumulative dose (mg)/ number of doses scheduled per protocol during treatment period (i.e., this is equivalent to planned dose level);
- **RDI (%):**
 - For MCS110: $100 \times \text{DI (mg/kg/3wks)}/\text{PDI (mg/kg/3wks)}$
 - For PDR001: $100 \times \text{DI (mg/3wks)}/\text{PDI (mg/3wks)}$

Note: If a patient is still on treatment at the time of data cut-off, the end date of study treatment/drug will be replaced by the data cut-off date and the above respective algorithm will be used.

Dose interruption: Actual dose equal to zero, between the first and last non-zero doses, following a non-zero actual dose.

Dose reduction: A non-zero actual dose that is less than the immediate previous non-zero actual dose (if not the first dose) and below the treatment received dose.

Note: actual dose for MCS110 (mg/kg) = Dose prescribed (mg/kg) * Total volume administered (ml)/Total volume planned to be administered (ml); actual dose for PDR001 (mg) = Dose prescribed (mg) * Total volume administered(ml)/Total volume planned to be administered(ml).

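### The SAP has no rule for patients whose dose is raised after 6 months: all Phase Ib data stay under the assigned dose, and a step back from an escalated dose is not counted as a reduction

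*SAP*

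**What the plan says.** Protocol 6.2.3.2: "Intra-patient dose escalation is not permitted at any time within the first 6 months of treatment". After that a patient may move to a higher, already evaluated dose pair, one drug at a time, under tolerability conditions and after consulting the sponsor. Further increases are allowed: "There is no limit to the number of times a patient may have his or her treatment dose increased".

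The SAP attributes data to dose as follows:
- Section 2.1, on Phase Ib: "All summaries, listings, figures and analyses will be performed by treatment group and" an all-subjects column.
- Section 2.2.1, on the FAS: "Patients will be analyzed according to the planned treatment combination". Section 2.4.1 adds: "Planned treatment is the treatment to which a patient is assigned during enrollment".
- Section 2.2.2, on the Safety Set: "The treatment assigned if it was received at least once, or" otherwise the first treatment given.
- Sections 2.1.1 and 2.8: the on-treatment period ends 30 days after the last dose, with no break when the dose level changes.
- Section 2.4.1, on dose reduction: the dose must be lower than the preceding non-zero dose "and below the treatment received dose". For the meaning of that term the same section says "Received treatment: Please refer to" Section 2.2.2, which means the assigned dose.

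The only SAP rule for a patient given two dose levels is in 2.5.2.1.1. It covers the first two cycles, for the dose-escalation model.

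**The concern.** AEs, dose reductions, interruptions and dose intensity are Phase Ib primary variables (SAP 2.5.1.1). Phase Ib exists to describe them by dose level. Where the protocol permits escalation within a patient, the plan has to say which dose a later event belongs to. This one does not, so an event that starts at an escalated dose is tabulated under the lower assigned dose.

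Protocol 6.2.3.2 lets a patient escalate only after at least two cycles at the lower dose without possibly related toxicity of Grade 2 or more. The tables would therefore charge later toxicity to a dose the patient had already tolerated.

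The reduction rule is more than a missing detail. It is a written definition that returns zero when a patient is brought back from an escalated dose.

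**Working it through.** The plan states no figure on this point, so there is none to reproduce. The check applies the SAP definitions to example dose paths and compares the earliest escalation with each endpoint's window.

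**1. Reduction rule.** Each illustrative path has 17 doses, the first 9 at the assigned level. The SAP rule needs dose < previous dose and dose < assigned dose. The plain rule needs only the first condition. RDI = 100 × sum of doses / (17 × assigned dose), since SAP 2.4.1 makes planned dose intensity equal to the planned dose level.

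| Path (number of doses at each level) | SAP count | Plain count | RDI |
|---|---|---|---|
| MCS110 1→3→1 mg/kg (9, 4, 4) | 0 | 1 | 25/17 = 147% |
| MCS110 3→5→3 mg/kg (9, 4, 4) | 0 | 1 | 59/51 = 116% |
| MCS110 1→3→5→3 mg/kg (9, 3, 3, 2) | 0 | 1 | 39/17 = 229% |
| PDR001 100→300→100 mg (9, 4, 4) | 0 | 1 | 2500/1700 = 147% |
| MCS110 3→5→1 mg/kg (9, 4, 4) | 1 | 1 | 51/51 = 100% |
| MCS110 3→1 mg/kg (9, 8) | 1 | 1 | 35/51 = 69% |

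Every return to the assigned dose, or to a level still above it, is missed. A drop below the assigned dose is counted.

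**2. Timing.** Six months = 6 × 30.4375 = 182.6 days. With 21-day cycles, CnD1 falls on day 21(n − 1) + 1. C9D1 is day 169 and C10D1 is day 190, so the first possible escalated dose is about C10.

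| Output | Latest day | Can follow escalation? |
|---|---|---|
| DLTs, dose-escalation model, MTD | 42 | No |
| PK, cycles 1 and 4 | 84 | No |
| Stable disease of 16 weeks (SAP 2.7.2) | 112 | No |
| Scans at C3, C5, C7, C9 | 43, 85, 127, 169 | No |
| Responses first seen at C12 or later | from 232 | Yes |
| AEs, labs, exposure, reductions after month 6 | open | Yes |
| PFS, DOR, OS | open | Yes |

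One edge case: a response first seen at C9 needs confirmation at least 4 weeks later (169 + 28 = day 197), which can fall after an escalated dose.

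**3. Size.** The Amendment 04 study status gives Phase Ib group sizes of 6, 12, 12, 13, 6 and 11. One patient with a misattributed event moves a group's incidence by 1/13 = 7.7 to 1/6 = 16.7 percentage points. The 1 mg/kg + 100 mg group has 6 patients.

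**The case against.** **Analysis by assigned dose is conventional.** This stands, and those tables should remain the main presentation. It does not remove the need for a supplementary rule where the protocol expressly permits escalation.

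**The data are not hidden.** SAP 2.4.1 lists all doses with reasons for change and has an RDI category of 1.1 and above, and SAP 2.8.1 lists all AEs. This largely stands: four of the five escalated paths above would fall in that category. But RDI cannot place an AE at a dose, the 3→5→1 path averages 100%, and a listing does not correct a summary count.

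**The reduction clause has a purpose.** Under assigned-dose grouping it keeps a step-back from 3 to 1 mg/kg from being charged to the 1 mg/kg group. Also, actual dose is derived from the volume infused, so without the clause a small shortfall in volume could register as a reduction. Both points stand. Simply deleting the clause would be wrong.

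**Dose at onset is an imperfect attribution.** Protocol 6.2.4 notes the long latency of some immune-related events, so an event after escalation may reflect earlier exposure. This stands as a limitation of any supplementary table.

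**A stronger reading is tempting:** that Phase Ib by-dose results are in fact contaminated, and that the durable control reported at 1 mg/kg, the ground for the lower-dose pancreatic group, reflects higher doses. The documents do not support it. No section reports an escalated patient. The Amendment 04 rationale gives 1 PR and 2 SD beyond a year at 1 mg/kg. The two SD patients passed month 6, but nothing says that they met the escalation conditions or changed dose. Amendment 05 says that the expansion criteria were not met and enrolment is closed, so no Group 2b decision is pending.

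**Conclusion.** The point holds as a conditional gap with one definite error. The definite error is the reduction rule: as written it returns zero for any step-back to or above the assigned dose, in a Phase Ib primary tolerability variable. The conditional gap is attribution. If anyone was escalated, AEs, labs and exposure after about month 6, and PFS, DOR, OS and late responses, are credited to a dose lower than the one in force. One such patient is worth up to 16.7 percentage points of incidence in a 6-patient group.

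Dose selection is not touched: DLTs, the dose-escalation model and MTD, cycle 1 and 4 PK, the 16-week threshold and scans through C9 all precede escalation. A reader might infer that higher-dose intolerance is concealed altogether. The dose listing and RDI rule that out; what is missing is a summary count tied to the dose in force.

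Assumptions: 21-day cycles without delay (an escalated dose before the C9 scan would need the C8 dose, day 148, to slip by 183 − 148 = 35 days), and at least one escalated patient for the attribution part. The number escalated is unknown from the documents, but Protocol 6.2.3.2 requires these changes on the dosing record, so the sponsor can count them.

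**What to change.** Amend the SAP, or add an addendum, and keep the assigned-dose tables as the main presentation:

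1. Report the number of patients escalated in each Phase Ib group, and list them with dates and dose pairs. If there were none, one sentence closes the attribution question; the reduction definition should still be corrected.
2. Flag AEs with onset on or after the first escalated dose. Add a supplementary by-dose safety summary that stops the day before first escalation, with later events shown separately by the dose pair in force at onset.
3. Count any decrease in dose level from the previous dose as a reduction, in two rows: below the assigned dose; and from an escalated dose to a level at or above the assigned dose. Attribute the second row to the escalated dose pair. Base the count on dose level so that small infusion-volume differences do not register.
4. Optional: PFS and DOR censored at first escalation, labelled as potentially informatively censored, because only patients still on treatment and tolerating it after 6 months can be escalated.

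Cost: some extra programming from dosing data already collected, shorter exposure in the supplementary tables, and imperfect attribution of late-onset immune-related events. No new data are needed and no dosing rule changes.
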